10.3.2 Definition of SAE

An SAE is defined as any untoward medical occurrence that, at any dose, meets 1 or more of the criteria listed:

A) Results in death

B) Is life-threatening

The term *life-threatening* in the definition of *serious* refers to an event in which the participant was at risk of death at the time of the event. It does not refer to an event, which hypothetically might have caused death, if it were more severe.

C) Requires inpatient hospitalization or prolongation of existing hospitalization

- In general, hospitalization signifies that the participant has been admitted (usually involving at least an overnight stay) at the hospital or emergency ward for observation and/or treatment that would not have been appropriate in the physician's office or outpatient setting. Complications that occur during hospitalization are AEs. If a complication prolongs hospitalization or fulfills any other serious criteria, the event is serious. When in doubt as to whether hospitalization occurred or was necessary, the AE should be considered serious.
- Hospitalization for elective treatment of a pre-existing condition that did not worsen from baseline is not considered an AE.

D) Results in persistent or significant disability/incapacity

- The term disability means a substantial disruption of a person's ability to conduct normal life functions.
- This definition is not intended to include experiences of relatively minor medical significance such as uncomplicated headache, nausea, vomiting, diarrhea, influenza, and accidental trauma (eg, sprained ankle) that may interfere with or prevent everyday life functions but do not constitute a substantial disruption.

E) Is a congenital anomaly/birth defect

F) Other situations:

- Medical or scientific judgment should be exercised by the Investigator in deciding whether SAE reporting is appropriate in other situations such as important medical events that may not be immediately life-threatening or result in death or hospitalization but may jeopardize the participant or may require medical or surgical intervention to prevent one of the other outcomes listed in the above definition. These events should usually be considered serious.
 - The following list of medically important events is intended to serve as a guideline for determining which condition has to be considered as a medically important event. The list is not intended to be exhaustive:
 - Intensive treatment in an emergency room or at home for:
 - Allergic bronchospasm.

- Blood dyscrasias (ie, agranulocytosis, aplastic anemia, bone marrow aplasia, myelodysplasia, pancytopenia, etc).
- Convulsions (seizures, epilepsy, epileptic fit, absence, etc).
- Development of drug dependence or drug abuse.
- $ALT > 3 \times ULN$ + total bilirubin $> 2 \times ULN$ or asymptomatic ALT increase $> 10 \times ULN$.
- Suicide attempt or any event suggestive of suicidality.
- Syncope, loss of consciousness (except if documented as a consequence of blood sampling).
- Bullous cutaneous eruptions.

10.3.3 Recording and follow-up of AE and/or SAE

AE and SAE recording

- When an AE/SAE occurs, it is the responsibility of the Investigator to review all documentation (eg, hospital progress notes, laboratory reports, and diagnostics reports) related to the event.
- The Investigator will then record all relevant AE/SAE information.
- It is **not** acceptable for the Investigator to send photocopies of the participant's medical records to the Sponsor's representative in lieu of completion of the required form.
- There may be instances when copies of medical records for certain cases are requested by the Sponsor's representative. In this case, all participant identifiers, with the exception of the participant number, will be redacted on the copies of the medical records before submission to the Sponsor's representative.
- The Investigator will attempt to establish a diagnosis of the event based on signs, symptoms, and/or other clinical information. Whenever possible, the diagnosis (not the individual signs/symptoms) will be documented as the AE/SAE.

Assessment of intensity

The Investigator will make an assessment of intensity for each AE and SAE reported during the study and assign it to 1 of the following categories:

- **Mild:** A type of adverse event that is usually transient and may require only minimal treatment or therapeutic intervention. The event does not generally interfere with usual activities of daily living.
- **Moderate:** A type of adverse event that is usually alleviated with additional specific therapeutic intervention. The event interferes with usual activities of daily living, causing discomfort but poses no significant or permanent risk of harm to the research participant.
- **Severe:** A type of adverse event that interrupts usual activities of daily living, or significantly affects clinical status, or may require intensive therapeutic intervention.

Assessment of causality

- The Investigator is obligated to assess the relationship between study intervention and each occurrence of each AE/SAE. The Investigator will use clinical judgment to determine the relationship.
- *A reasonable possibility* of a relationship conveys that there are facts, evidence, and/or arguments to suggest a causal relationship, rather than that a relationship cannot be ruled out.
- Alternative causes, such as underlying disease(s), concomitant therapy, and other risk factors, as well as the temporal relationship of the event to study intervention administration will be considered and investigated.
- For causality assessment, the Investigator will also consult the IB and/or product information, for marketed products.
- The Investigator must review and provide an assessment of causality for each AE/SAE and document this in the medical notes. There may be situations in which an SAE has occurred and the Investigator has minimal information to include in the initial report to the Sponsor's representative. However, **it is very important that the Investigator always make an assessment of causality for every event before the initial transmission of the SAE data to the Sponsor's representative.**
- The Investigator may change his/her opinion of causality in light of follow-up information and send an SAE follow-up report with the updated causality assessment.
- The causality assessment is one of the criteria used when determining regulatory reporting requirements.

Follow-up of AEs and SAEs

- The Investigator is obligated to perform or arrange for the conduct of supplemental measurements and/or evaluations as medically indicated or as requested by the Sponsor's representative to elucidate the nature and/or causality of the AE or SAE as fully as possible. This may include additional laboratory tests or investigations, histopathological examinations, or consultation with other health care professionals.
- If a participant dies during participation in the study or during a recognized follow-up period, the Investigator will provide the Sponsor with a copy of any postmortem findings including histopathology, if available.
- New or updated information will be recorded in the originally submitted documents.
- The Investigator will submit any updated SAE data to the Sponsor within 24 hours of receipt of the information.

10.3.4 Reporting of SAEs

SAE reporting to the Sponsor via an electronic data collection tool

- The primary mechanism for reporting an SAE to the Sponsor's representative will be the electronic data collection tool.
- If the electronic system is unavailable, then the site will use the paper SAE data collection tool (see next section) to report the event within 24 hours.
- The site will enter the SAE data into the electronic system as soon as it becomes available.
- After the study is completed at a given site, the electronic data collection tool will be taken offline to prevent the entry of new data or changes to existing data.
- If a site receives a report of a new SAE from a study participant or receives updated data on a previously reported SAE after the electronic data collection tool has been taken offline, then the site can report this information on a paper SAE form (see next section) or to the Sponsor's representative by telephone.
- Contacts for SAE reporting can be found in the ISF.

SAE reporting to the Sponsor via paper data collection tool

- Facsimile transmission of the SAE paper data collection tool is the preferred method to transmit this information to the Sponsor's representative.
- In rare circumstances and in the absence of facsimile equipment, notification by telephone is acceptable with a copy of the SAE data collection tool sent by overnight mail or courier service.
- Initial notification via telephone does not replace the need for the Investigator to complete and sign the SAE data collection tool within the designated reporting timeframes.
- Contacts for SAE reporting can be found in contact list in the ISF.

10.4 APPENDIX 4: CONTRACEPTIVE AND BARRIER GUIDANCE

10.4.1 Definitions

Woman of childbearing potential

A woman is considered fertile following menarche and until becoming postmenopausal unless permanently sterile (see below).

If fertility is unclear (eg, amenorrhea in adolescents or athletes) and a menstrual cycle cannot be confirmed before first dose of study intervention, additional evaluation should be considered.

Women in the following categories are not considered WOCBP.

1. Premenarchal.

2. Premenopausal female with 1 of the following:
 - Documented hysterectomy.
 - Documented bilateral salpingectomy.
 - Documented bilateral oophorectomy.
 - For individuals with permanent infertility due to an alternate medical cause other than the above, (eg, Mullerian agenesis, androgen insensitivity), Investigator discretion should be applied to determining study entry.

Note: Documentation can come from the site personnel's: review of the participant's medical records, medical examination, or medical history interview.

3. Postmenopausal female.
 - A postmenopausal state is defined as no menses for 12 months without an alternative medical cause.
4. A high FSH level in the postmenopausal range may be used to confirm a postmenopausal state in women not using hormonal contraception or HRT. However, in the absence of 12 months of amenorrhea, confirmation with more than one FSH measurement is required.
5. Females on HRT and whose menopausal status is in doubt will be required to use one of the non-estrogen hormonal highly effective contraception methods if they wish to continue their HRT during the study. Otherwise, they must discontinue HRT to allow confirmation of postmenopausal status before study enrollment.

10.4.2 Contraception guidance

Female participants of childbearing potential are eligible to participate if they agree to use a method of contraception consistently and correctly as described below.

CONTRACEPTIVES^a ALLOWED DURING THE STUDY INCLUDE:

Highly Effective Methods^b That Have Low User Dependency

- Implantable progestogen-only hormone contraception associated with inhibition of ovulation^c
- IUD
- IUS^c
- Bilateral tubal occlusion.
- Vasectomized partner.

(Vasectomized partner is a highly effective contraceptive method provided that the partner is the sole sexual partner of the WOCBP and the absence of sperm has been confirmed. If not, an additional highly effective method of contraception should be used. Spermatogenesis cycle is approximately 90 days.)

Highly Effective Methods^b That Are User Dependent

- Combined (estrogen- and progestogen-containing) hormonal contraception associated with inhibition of ovulation^c
 - Oral
 - Intravaginal
 - Transdermal
 - Injectable.
-

-
- Progestogen-only hormone contraception associated with inhibition of ovulation^C
 - Oral
 - Injectable.
 - Sexual abstinence.

(Sexual abstinence is considered a highly effective method only if defined as refraining from heterosexual intercourse during the entire period of risk associated with the study intervention. The reliability of sexual abstinence needs to be evaluated in relation to the duration of the study and the preferred and usual lifestyle of the participant.)

Abbreviations: CTFG = clinical trial facilitation group; IUD = intrauterine device; IUS = intrauterine hormone-releasing system; LAM = lactational amenorrhea method.

- a Contraceptive use by men or women should be consistent with local regulations regarding the use of contraceptive methods for those participating in clinical studies.
- b Failure rate of <1% per year when used consistently and correctly. Typical use failure rates differ from those when used consistently and correctly.
- c Male condoms must be used in addition to hormonal contraception. If locally required, in accordance with CTFG guidelines, acceptable contraceptive methods are limited to those which inhibit ovulation as the primary mode of action.

Note: Periodic abstinence (calendar, symptothermal, post-ovulation methods), withdrawal (coitus interruptus), spermicides only, and LAM are not acceptable methods of contraception for this study. Male condom and female condom should not be used together (due to risk of failure with friction).

10.5 APPENDIX 5: GENETICS

[figure not shown]
Use/Analysis of RNA and/or DNA

- Genetic variation may impact a participant's response to study intervention, susceptibility to, and severity and progression of disease. Variable response to study intervention may be due to genetic determinants that impact drug absorption, distribution, metabolism, and excretion; mechanism of action of the drug; disease etiology; and/or molecular subtype of the disease being treated. Therefore, where local regulations and IRB/IEC allow, a blood sample will be collected for DNA analysis from consenting participants.
- RNA and DNA samples will be used for research related to itepekimab or CRSwNP and related diseases. They may also be used to develop tests/assays including diagnostic tests related to itepekimab and/or interventions of this drug class and CRSwNP. Genetic research may consist of the analysis of one or more candidate genes or the analysis of genetic markers throughout the genome, and/or RNA sequencing to determine expression levels of gene(s) of interest.
- RNA and DNA samples will be used for research related to itepekimab or CRSwNP and related diseases. They may be used to determine a possible relationship between gene expression levels (RNA) or gene variants (DNA) and response to treatment with itepekimab, how the body processes itepekimab and possible side effects of itepekimab. Additional analyses may be conducted if it is hypothesized that this may help further understand the clinical data.
- The DNA and RNA samples may be analyzed as part of a multi-study assessment of genetic or transcriptomic factors involved in the response to itepekimab or study interventions of this class to understand the study disease or related conditions.
- The results of genetic analyses may be reported in the CSR or in a separate study summary.

- The Sponsor will store the RNA and DNA samples in a secure storage space with adequate measures to protect confidentiality.
- The samples will be retained while research on itepekimab and/or study interventions of this class or CRSwNP continues but no longer than 25 years or other period as per local requirements.

10.6 APPENDIX 6: LIVER AND OTHER SAFETY: ACTIONS AND FOLLOW-UP ASSESSMENTS

[figure not shown]
NEUTROPENIA

[figure not shown]
* For individuals of African descent, the relevant value of concern is $<1000/\text{mm}^3$

Neutropenia is to be recorded as an AE only if at least 1 of the criteria listed in the general guidelines for reporting adverse events in [Section 10.3](#) is met.

THROMBOCYTOPENIA

Thrombocytopenia is to be recorded as an AE only if at least 1 of the criteria listed in the general guidelines for reporting adverse events in [Section 10.3](#) is met.

*If unable to retest in 72 hours, use original lab results to decide on further reporting/monitoring/discontinuation.

** Unless a protocol-defined criterion for permanent discontinuation is met.

*** See box below.

[figure not shown]
Note:

- “Baseline” refers to ALT sampled at baseline visit; or if baseline value unavailable, to the latest ALT sampled before the baseline visit. The algorithm does not apply to the instances of increase in ALT during screening.
- See [Section 10.3](#) for guidance on safety reporting.

Evaluate Increase in ALT***

[figure not shown]
1. **INFORM** the Site Monitor who will forward the information to the Study Manager
2. **INVESTIGATE** specifically for malaise with or without loss of consciousness, dizziness, and/or hypotension and/or episode of arrhythmia in the previous 72 hours; rule out muscular injury
3. **INVESTIGATE** if any recent alcohol use or travel
4. **INVESTIGATE** if any use of non-prescription medications including herbal or dietary supplements
5. **PERFORM** the following tests:
 - LFTs: AST, ALT, alkaline phosphatase, GGT, total and conjugated bilirubin and prothrombin time / INR
 - CPK, serum creatinine, complete blood count
 - Anti-HAV IgM, anti-HBc IgM, (HBV-DNA if clinically indicated), anti-HCV and HCV RNA, anti-CMV IgM and anti-HEV IgM antibodies
 - Depending on the clinical context, check for recent infection with EBV, herpes viruses, and toxoplasma
 - Hepatobiliary ultrasonography (or other imaging investigations if needed)
6. **CONSIDER** Auto-antibodies: antinuclear, anti-DNA, anti-smooth muscle, anti-LKM
7. **CONSIDER** iron, ferritin and transferrin
8. **CONSIDER** biomarkers for alcohol use (eg, urine ethyl glucuronide (EtG))
9. **CONSIDER** consulting with hepatologist
10. **CONSIDER** patient hospitalization if INR>2 (or PT<50%) and/or central nervous system disturbances suggesting hepatic encephalopathy
11. **MONITOR LFTs after discontinuation of IMP:**
 - *As closely as possible* (or **every 48 hours**) until stabilization, then every 2 weeks until return to \leq ULN, baseline value (if baseline >ULN) or clinical resolution.
12. **FREEZE** serum sample (5ml x 2)
13. **In case of suspicion of GILBERT Syndrome**, a DNA diagnostic test should be done

**INCREASE IN SERUM CREATININE in patients with normal baseline
(creatininemia between 45 µmol/L and 84 µmol/L)**

Increase in serum creatinine is to be recorded as an AE only if at least 1 of the criteria listed in the general guidelines for reporting adverse events in [Section 10.3](#) is met.

INCREASE IN CPK OF NON-CARDIAC ORIGIN AND NOT RELATED TO INTENSIVE PHYSICAL ACTIVITY

Increase in creatine phosphokinase (CPK) is to be recorded as an AE only if at least 1 of the criteria in the general guidelines for reporting adverse events in [Section 10.3](#) is met.

10.7 APPENDIX 7: MEDICAL DEVICES AES, ADES, SAES, SADES, USADES AND DEVICE DEFICIENCIES: DEFINITIONS AND PROCEDURES FOR RECORDING, EVALUATING, FOLLOW-UP, AND REPORTING IN MEDICAL DEVICE STUDIES

The definitions and procedures detailed in this appendix are in accordance with ISO 14155 and the European Medical Device Regulation (MDR) 2017/745 for clinical device research (if applicable).

Both the Investigator and the Sponsor will comply with all local medical device reporting requirements for medical devices.

The detection and documentation procedures described in this protocol apply to all Sponsor medical devices provided for use in the study (see [Section 6.1.4](#)) for the list of Sponsor medical devices).

10.7.1 Definition of medical device AE and ADE

Medical device AE and ADE definition

- A medical device AE is any untoward medical occurrence in a clinical study participant, users, or other persons, temporally associated with the use of study intervention, whether or not considered related to the investigational medical device. An AE can therefore be any unfavorable and unintended sign (including an abnormal laboratory finding), symptom, or disease (new or exacerbated) temporally associated with the use of an investigational medical device. This definition includes events related to the investigational medical device or comparator and events related to the procedures involved except for events in users or other persons, which only include events related to investigational devices.
- An ADE is defined as an AE related to the use of an investigational medical device. This definition includes any AE resulting from insufficient or inadequate instructions for use, deployment, implantation, installation, or operation, or any malfunction of the investigational medical device as well as any event resulting from use error or from intentional misuse of the investigational medical device.

10.8 APPENDIX 8: COUNTRY-SPECIFIC/REGION REQUIREMENTS

10.8.1 China

China participants should be on daily treatment with INCS prior to screening and will continue their daily INCS with a stable dose as background treatment during the screening and throughout the study.

Genetic analyses as described in [Section 8.7](#) will be optional for participants enrolled in China. All biomarkers (except for blood neutrophil and eosinophil count) can be considered optional in China.

Future use of biological samples as described in [Section 8.11](#) is not applicable for participants in China.

10.8.2 Japan

In Japan, participants on INCS (MFNS or other INCS) will continue taking their daily INCS with a stable dose through all periods of the study. In Japan, participants not on INCS prior to screening, will receive MFNS during screening and throughout the study.

10.8.3 Germany

Informed consent process: all references to "legally authorized representative" are not applicable in Germany; only participants who can give written consent themselves are included in the study. References to "legally authorized representative" are found in [Section 7.1.1](#), [Section 8.4](#), [Section 8.4.7](#), and [Section 10.9](#).

10.8.4 France

Exclusion criterion specific to France:

E 32. The participant is not affiliated to a social security scheme.

E 33. The participant is under tutorship or curatorship; the participant is under safeguard of justice or deprived of his/her liberty by an administrative or court decision.

10.8.5 Czechia

In addition to E 23, the following is required for Czechia (see underlined text): participants from Czechia with a positive TB skin test or a positive Quantiferon assay are excluded from the study unless all of the following conditions are met:

- Have a history of completed chemoprophylaxis for latent TB infection (with a treatment regimen as per local guidelines), OR has completed treatment for active TB infection (with a treatment regimen as per local guidelines),
AND
- Have obtained consultation with a specialist to rule out active and latent TB infection,
AND
- For whom review and approval from Sponsor has been granted.

In addition to E 20, the following is required for participants randomized in Czechia:

1. If a participant has anti-HBc Ab positivity at screening but is confirmed to have no detectable HBV DNA by PCR testing at screening, the participant must be willing to have repeat HBV DNA PCR testing performed at least every 3 months until the end of trial.

2. If a participant has anti-HBs Ab positivity at screening but is confirmed to have no detectable HBV DNA by PCR testing at screening, the participant must be willing to repeat HBV DNA PCR testing performed at least every 3 months until the end of trial, unless the participant has completed HBV vaccination previously as proven by medical records.
3. If a participant has total anti-HCV Ab positivity at screening but is confirmed to have no detectable HCV RNA by PCR testing, the participant will repeat HCV RNA PCR testing at least every 3 months until the end of trial.

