- E 17. Participants treated with INCS (MFNS is permitted), intranasal emitting devices/stents, nasal spray using exhalation delivery system such as Xhance™ during the screening period. In Japan and China INCS other than MFNS are permitted.
- E 18. Participants receiving leukotriene antagonists/modifiers unless a participant is on a stable dose for at least 30 days prior to Visit 1.

- E 19. Exposure to another investigative drug (mAb as well as small molecules) prior to Screening (Visit 1), within the period specified as follows: an interval of less than 6 months or <5 PK half-lives for investigative mAb, and an interval of less than 30 days or <5 PK half-lives, whichever is longer, for investigative small molecules.
- E 20. Participants who have undergone any sinus intranasal surgery (including polypectomy) within 6 months before Visit 1.
- E 21. Participants who have had a sinonasal surgery changing the lateral wall structure of the nose making impossible the evaluation of NPS.
- E 22. Participants who received SCS 1 month prior to Screening (Visit 1) or during the screening period (between Visit 1 and Visit 2).

Prior/concurrent clinical study experience

- E 23. Participant who has previously participated in itepekimab clinical trials.
- E 24. Known allergy to itepekimab or its excipients, or any drug or other allergy that, in the opinion of the Investigator, contraindicates participation in this study.

Diagnostic assessments

- E 25. Clinically significant laboratory tests at Screening (Visit 1):
 - ALT or AST >2 times ULN.
 - Hemoglobin <10 g/100 mL for male and <9 g/100 mL for female.
 - Neutrophils <1500/mm³ (<1000/mm³ for those of African descent).
 - Platelets <100 000/mm³.
 - Creatinine >150 µmol/L.
- E 26. Participants with any of the following result at Screening (Visit 1): positive (or indeterminate) hepatitis B surface antigen (HBsAg) or positive IgM HBcAb or positive total HBcAb confirmed by positive HBV DNA or positive HCV Ab confirmed by positive HCV RNA.
- E 27. History of HIV infection or positive HIV 1/2 serology at Screening (Visit 1).

Noncompliance to completion of the e-diary

- E 28. Participants must demonstrate at least the following for acceptable compliance: completing the eDiary for any 4 in the 7 days immediately preceding the Baseline Visit (Visit 2).

Other exclusion criteria

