8.3.4 Clinical safety laboratory tests

- See Appendix 2 ([Section 10.2](#)) for the list of clinical laboratory tests to be performed and to the SoA ([Section 1.3](#)) for the timing and frequency.
- The Investigator must review the laboratory results, document this review, and record any clinically significant changes occurring during the study as an AE. The laboratory results must be retained with source documents. See Appendix 3 ([Section 10.3](#)) for abnormal laboratory results reporting. All laboratory tests with values considered clinically significantly abnormal during participation in the study or within 20 weeks after the last dose of study intervention should be repeated until the values return to normal or baseline or are no longer considered clinically significant by the Investigator.
 - If clinically significant values do not return to normal/baseline within a period of time judged reasonable by the Investigator, the etiology should be identified and the Sponsor notified.
 - All protocol-required laboratory tests, as defined in Appendix 2 ([Section 10.2](#)), must be conducted in accordance with the laboratory manual and the SoA ([Section 1.3](#)).
 - If laboratory values from non-protocol specified laboratory tests performed at the institution's local laboratory require a change in participant management or are considered clinically significant by the Investigator (eg, SAE or AE or dose modification), then the results must be recorded in the eCRF.
 - Critical values alerts are linked to extremely high or low laboratory test values which are considered to be potentially life-threatening. In case of abnormal lab value, the Central Laboratory will contact the site.
 - Special procedures for collection, storage, and shipping of serum are described in the Central Laboratory Manual.
 - At Screening, hepatitis serology testing is performed in order to rule out active or chronic infection. Guidance on hepatitis serology eligibility interpretation is provided in [Table 8](#).

Table 8 - Hepatitis serology testing

Hepatitis serology result	Protocol action
HBsAg: positive or indeterminate	Excluded
HBsAb positive, HBsAg negative, HBcAb: negative	Eligible
HBcAb IgM: positive	Excluded
HBcAb Total: positive (with or without HBsAb positive)	Test for HBV DNA If HBV DNA Positive: Excluded If HBV DNA Indeterminate: Eligible
HCV antibody: positive	Test for HCV RNA If HCV RNA Positive: Excluded If HCV RNA Indeterminate: Eligible

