Abbreviations: DNA = deoxyribonucleic acid; HBcAb = hepatitis B core antibody; HBsAg = hepatitis B surface antigen; HBV = hepatitis B virus; HBsAb = hepatitis B surface antibody; HCV = hepatitis C virus; Ig = immunoglobulin; RNA = ribonucleic acid.
See [Section 10.8.5](#) for country-specific requirements for Czechia.

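### Table 8 makes an indeterminate HBV DNA or HCV RNA result eligible and lists no negative outcome, so an unresolved PCR can be randomized with no required repeat

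*Protocol*

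**What the plan says.** Protocol Section 8.3.4 says that at screening "hepatitis serology testing is performed in order to rule out active or chronic infection". Table 8 then gives the action for each result:

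- HBsAg: "HBsAg: positive or indeterminate" leads to exclusion.
- Total HBcAb positive: test HBV DNA, then "If HBV DNA Positive: Excluded If HBV DNA Indeterminate: Eligible".
- HCV antibody positive: test HCV RNA, then "If HCV RNA Positive: Excluded If HCV RNA Indeterminate: Eligible".

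Neither PCR row has an entry for a negative or undetected result. Exclusion criterion E 26 (Section 5.2) also excludes a positive or indeterminate HBsAg, but for the PCR step it names only "positive total HBcAb confirmed by positive HBV DNA or positive HCV Ab confirmed by positive HCV RNA". Footnote t of the Schedule of Activities and Table 12 in Appendix 2 explain the PCR: it is there to detect a false-positive antibody and, for HBV, to settle what the serology means before randomization.

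The note under Table 8 refers to Section 10.8.5 "for country-specific requirements for Czechia". That section requires a repeat PCR at least every 3 months. Item 1 begins "If a participant has anti-HBc Ab positivity at screening but is confirmed to have no detectable HBV DNA by PCR testing at screening". Item 3 applies to an HCV-antibody-positive participant "confirmed to have no detectable HCV RNA by PCR testing". The section presents its TB rule as an addition to E 23 and its hepatitis rule as an addition to E 20.

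**The concern.** A reflex PCR is done because the antibody result alone does not show whether the participant is infected. An indeterminate PCR leaves that question open, yet Table 8 treats it as sufficient for entry. The ordinary outcome, nucleic acid not detected, is the one the table leaves out. The protocol is stricter one step earlier, where an indeterminate HBsAg excludes.

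What is at stake is participant safety. Section 2.3.1 names serious infection as an important potential risk of itepekimab, and Table 1 lists the hepatitis exclusion among the mitigations. A participant whose viral status is unresolved could start up to 52 weeks of treatment with no repeat PCR required. Sites could also decide such cases differently, because the table and the purpose of the test point in different directions.

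**Working it through.** This is mainly a comparison of texts. The protocol states no figure to reproduce.

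**Step 1. Follow an antibody-positive participant (total HBcAb or HCV antibody) through each PCR result.**

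| PCR result | Table 8 | E 26 | Czech retest (10.8.5, items 1 and 3) |
|---|---|---|---|
| Positive | Excluded | Excluded | Not reached |
| Not detected | Not listed | Not excluded | At least every 3 months |
| Indeterminate | Eligible | Not excluded | Not triggered |

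The bottom row is the gap. Table 8 and E 26 both let the participant in. The Czech rule does not apply, because an indeterminate result does not confirm that nothing was detected.

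**Step 2. Look for another required repeat.** Viral hepatitis testing is scheduled at screening only. Outside Section 10.8.5, the readable text of Appendix 6 (Section 10.6) lists hepatitis tests in the work-up of an ALT increase, with HBV DNA only if clinically indicated. Section 8 allows repeat or unscheduled samples for safety or technical reasons, so a repeat PCR is permitted but not required.

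**Step 3. Check the criterion numbers in Section 10.8.5 against Section 5.2.** E 23 is earlier participation in an itepekimab trial, whereas the TB criterion is E 04. E 20 is recent sinus surgery, whereas the hepatitis criterion is E 26.

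**Step 4. Size.** The protocol gives no antibody prevalence, no rate of indeterminate PCR and no Czech enrolment, so these are assumptions:

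- total HBcAb positive: 5% to 20%
- reflex PCR indeterminate: 1% to 5%
- Czech participants: 5 to 20

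With 210 participants, of whom 140 are planned on itepekimab (1:1:1 randomization):

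- Reflex HBV DNA tests: 210 × 0.05 = 10.5 to 210 × 0.20 = 42.
- Indeterminate, whole trial: 10.5 × 0.01 = 0.105 to 42 × 0.05 = 2.1.
- Of these on itepekimab: 140 × 0.05 × 0.01 = 0.07 to 140 × 0.20 × 0.05 = 1.4.
- In Czechia: 5 × 0.05 × 0.01 = 0.0025 to 20 × 0.20 × 0.05 = 0.2.

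HCV is not counted and would add to these.

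**The case against.** The strongest reply is that indeterminate is a one-word slip for negative. The missing negative outcome and the stated purpose of the PCR both support that. If so, the intended rule is sound and Section 10.8.5 has no gap. This may well be right, but sites apply the printed word, and E 26 does not correct it.

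The second reply is that the exposure is guarded. Anyone in this position has ALT and AST no higher than 2 × ULN at screening (E 25) and, in the HBV case, is negative for HBsAg and for IgM HBcAb (E 26). Clinical chemistry, including ALT, is scheduled at Weeks 12, 24, 36, 52 and 72, and Section 7.1.1 has mandatory ALT stopping rules. The investigator can exclude under E 01 or E 30, stop treatment, or take a repeat sample. All of this stands and lowers the risk. However, ALT is not a substitute for resolving a PCR, and none of these safeguards requires the repeat.

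Two stronger readings are tempting. One is that the Czech section itself is wrong because it follows cleared participants and leaves unresolved ones alone. The documents do not support this: the Czech sentences are reasonable as a national addition for undetected results, and the fault lies in Table 8. The other is that the wrong criterion numbers would lead sites astray. Each Czech paragraph names its own subject and Table 8 points to the section, so the numbers are clerical errors.

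**Conclusion.** The point holds and is minor. As written, Table 8 and E 26 admit an antibody-positive participant with an unresolved HBV DNA or HCV RNA result in any country. That conflicts with the stated purpose of the testing and with the treatment of an indeterminate HBsAg.

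The expected number is small: roughly 0.1 to 2.1 participants in the trial through HBV and close to none in Czechia, entirely on assumed rates. A reader might infer that infected participants will be enrolled or left unmonitored. The documents do not show that, since an indeterminate PCR is not evidence of infection and liver tests continue throughout.

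Endpoints, power and error control are not affected. Whether the word in Table 8 is deliberate or a slip cannot be settled from the protocol, but the same correction serves both cases.

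**What to change.** In Table 8, for HBV DNA and for HCV RNA, keep the exclusion for a positive result and add: *Not detected: Eligible; Indeterminate: repeat before randomization, eligible only if not detected.* Align E 26 so that a PCR not resolved as undetected also excludes. Items 1 and 3 of Section 10.8.5 then need no change, because every Czech participant admitted with positive total HBcAb or HCV antibody will have an undetected PCR and fall under the retest. In the same section, replace E 23 by E 04 and E 20 by E 26.

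If indeterminate was meant as written, the change tightens eligibility in all countries, so it is more than an editorial correction. The practical cost is one repeat PCR for each of the few indeterminate results, which Section 8 already permits, and an occasional extra screen failure. No change to the sample size or the analysis is needed.
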